7.5. FACIT-F Subscale

FACIT-F subscale is a 13-item instrument designed to assess fatigue/tiredness and its impact on daily activities and functioning in a number of chronic diseases. The 13 items are shown in [Figure 1](#), where the gray bar on the left is the item code. If 7 or more item scores are nonmissing, then the FACIT-F subscale score will be calculated as shown in [Figure 2](#); otherwise, the FACIT-F subscale score will be set to missing. Actual measurements, change, and percentage change from baseline will be summarized for the fatigue subscale score.

Figure 1: FACIT-F Subscale (Version 4)

Below is a list of statements that other people with your illness have said are important. **Please circle or mark one number per line to indicate your response as it applies to the past 7 days.**

		Not at all	A little bit	Some- what	Quite a bit	Very much
HI7	I feel fatigued	0	1	2	3	4
HI12	I feel weak all over	0	1	2	3	4
An1	I feel listless (“washed out”)	0	1	2	3	4
An2	I feel tired.....	0	1	2	3	4
An3	I have trouble starting things because I am tired.....	0	1	2	3	4
An4	I have trouble finishing things because I am tired	0	1	2	3	4
An5	I have energy	0	1	2	3	4
An7	I am able to do my usual activities	0	1	2	3	4
An8	I need to sleep during the day	0	1	2	3	4
An12	I am too tired to eat.....	0	1	2	3	4
An14	I need help doing my usual activities	0	1	2	3	4
An15	I am frustrated by being too tired to do the things I want to do	0	1	2	3	4
An16	I have to limit my social activity because I am tired.....	0	1	2	3	4

Figure 2: FACIT-F Subscale Calculation

Subscale	Item Code	Reverse item?	Item response	Item Score
FATIGUE SUBSCALE	HI7	4	-	= _____
	HI12	4	-	= _____
	An1	4	-	= _____
	An2	4	-	= _____
Score range: 0-52	An3	4	-	= _____
	An4	4	-	= _____
	An5	0	+	= _____
	An7	0	+	= _____
	An8	4	-	= _____
	An12	4	-	= _____
	An14	4	-	= _____
	An15	4	-	= _____
	An16	4	-	= _____

Sum individual item scores: _____
Multiply by 13: _____
Divide by number of items answered: _____

=Fatigue Subscale score

7.6. Pharmacokinetic Analyses

The data will be analyzed by standard population PK methods using appropriate software (eg, NONMEM®). An attempt will be made to evaluate the effect of demographic characteristics and baseline characteristics (eg, age, weight, sex, race, renal function) on the population PK profile. Additionally, exposure-response analyses for key efficacy and safety parameters may also be considered if there are sufficient data available.

7.7. Pharmacodynamic Analyses

Biomarkers from blood samples will be summarized using descriptive statistics by treatment group. Additionally, subgroup analysis will include participants with other baseline characteristics, including duration of autoimmune hemolytic anemia, concomitant autoimmune disease, and prior treatments.

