5. STUDY POPULATION

Participants with warm, cold (CAD), and mixed-type AIHA without an underlying lymphoproliferative malignancy compose the study population. Participants will be permitted to continue on a low dose (equivalent to ≤ 20 mg/day of prednisone) of corticosteroids or taper corticosteroids as appropriate.

Deviations from eligibility criteria are not allowed, because they can potentially jeopardize the scientific integrity of the study, regulatory acceptability, and/or participant safety. Therefore, adherence to the criteria as specified in the Protocol is essential.

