5.1. Inclusion Criteria

A participant who meets all of the following criteria may be included in the study:

- 1. Men or women, aged 18 years or older.
- 2. Diagnosis of AIHA based on the presence of hemolytic anemia and serological evidence of anti-erythrocyte antibodies, detectable by the DAT as follows:
 - a. Warm: DAT positive for IgG only or IgG plus C3d
 - b. Cold (CAD): DAT positive for C3d only, with cold agglutinins of I specificity
 - c. Mixed: DAT positive for IgG and C3d, with coexistence of warm autoantibodies and high titer cold agglutinins
- 3. Participants who have disease progression after treatment with standard therapies that are known to confer clinical benefit or who are intolerant to treatment. There is no limit to the number of prior treatment regimens.
- 4. Hemoglobin 7 to 10 g/dL (as determined by local laboratory).
- 5. No evidence of a lymphoproliferative malignancy or other autoimmune-related underlying conditions (eg, systemic lupus erythematosus, Castleman's disease, Sjögren's syndrome, or other autoimmune diseases).

- 6. ECOG performance status score of 0 to 2 (see Appendix C and Oken et al 1982).
- 7. Willingness to avoid pregnancy or fathering children based on the criteria below:
 - a. Woman of nonchildbearing potential (ie, surgically sterile with a hysterectomy and/or bilateral oophorectomy OR postmenopausal, defined by last menstrual period > 12 months before screening and confirmed by FSH).
 - b. Woman of childbearing potential who has a negative serum pregnancy test at screening and who agrees to take appropriate precautions to avoid pregnancy (with at least 99% certainty) from screening through at least 93 days after the last dose of study drug. Permitted methods that are at least 99% effective in preventing pregnancy (see Appendix A) should be communicated to the participant and her understanding confirmed.
 - c. Man who agrees to take appropriate precautions to avoid fathering children (with at least 99% certainty) from screening through at least 93 days after the last dose of study drug. Permitted methods that are at least 99% effective in preventing pregnancy (see Appendix A) should be communicated to the participant and his understanding confirmed.
- 8. Able to comprehend and willing to sign an ICF.
- 9. Willingness to receive PJP prophylaxis during the study period.

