2.2. Objectives and Endpoints

Objectives	Endpoints
Primary	

• To evaluate the efficacy of INCB050465 in the treatment of participants with AIHA.	
• Proportion of participants attaining a CR (defined as hemoglobin ≥ 12 g/dL not attributed to transfusion effect*) at any visit from Week 6 to Week 12.• Proportion of participants attaining a PR (defined as hemoglobin 10-12 g/dL or at least ≥ 2 g/dL increase from baseline not attributed to transfusion effect) at any visit from Week 6 to Week 12. 
*No transfusion effect definition: > 1 week since last transfusion.

• To evaluate the safety of INCB050465 administered as repeat doses in participants with AIHA.	
• Safety and tolerability will be assessed by monitoring AEs, measuring vital signs and ECGs, and conducting clinical laboratory blood and urine sample assessments.
Secondary	

• To further evaluate the efficacy of INCB050465 in the treatment of participants with AIHA.	
• Proportion of participants attaining a CR during postbaseline visits.• Proportion of participants attaining a PR during postbaseline visits.• Proportion of participants attaining a ≥ 2 g/dL increase in hemoglobin from baseline.• Mean, change, and percentage change from baseline of hemoglobin.• Proportion of participants requiring transfusions.• Proportion of participants who achieve normalization of hemolytic markers. (Hemolysis markers: hemoglobin, haptoglobin, LDH, reticulocyte count, total bilirubin, and direct/indirect bilirubin.)• Change of daily usage of prednisone.• FACIT-F subscale assessment.

• To evaluate the PK effects of INCB050465.	
• PK endpoints: C_{\max}, t_{\max}, C_{\min}, AUC_{0-t}, and CL/F.

Objectives	Endpoints

• To evaluate the PD effects of INCB050465.	
• Change from baseline in PD markers: reticulocyte count, DAT for IgG and C3b, cold agglutinin levels, haptoglobin, total bilirubin, direct/indirect bilirubin, LDH, and complement assessment (CH50, C3, and C4).

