5.2. Treatment Groups

This is a multicenter, open-label, increasing dose strength study of INCB050465 administered as 1 tablet QD. There are 2 cohorts and approximately 10 participants will be enrolled in Cohort 1, and approximately 15 participants in Cohort 2.

Cohort 1: INCB050465 1 mg QD for up to 12 weeks. At Week 6, participants who fulfill dose increase criteria (see definition below) will be offered INCB050465 2.5 mg QD for up to 6 weeks. If there are any tolerability issues in individual participants who received 2.5 mg, the dose may be decreased to 1 mg.

Cohort 2: INCB050465 2.5 mg QD for up to 12 weeks. If there are any tolerability issues in individual participants, the dose may be decreased to 1 mg.

Criteria for dose increase: (1) Continue to require transfusions by Week 6 visit, or (2) do not attain a meaningful clinical response (at least a stabilization ≥ 2 g/dL increase in hemoglobin from baseline to Week 6). Dose increases require sponsor preapproval (refer to Protocol, Section 6.6).

Participants will be summarized overall and based on the dose regimen initially assigned in the study.

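### SAP 7.7 plans a PD subgroup that eligibility leaves empty and does not name AIHA type, so a pooled DAT-IgG summary partly reflects case mix

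*SAP*

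**What the plan says.** The PD objective is secondary. Its endpoint is change from baseline in a set of markers that includes "DAT for IgG and C3b, cold agglutinin levels" (SAP 2.2), alongside reticulocytes, haptoglobin, bilirubin, LDH and complement.

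SAP 7.7 gives the method in two sentences. The first is: "Biomarkers from blood samples will be summarized using descriptive statistics by treatment group". SAP 5.2 explains the grouping: "Participants will be summarized overall and based on the dose regimen initially assigned in the study". The second names the subgroups: "subgroup analysis will include participants with other baseline characteristics, including duration of autoimmune hemolytic anemia, concomitant autoimmune disease, and prior treatments". AIHA type is not among them, although SAP 6.1.2 lists it as a baseline disease characteristic.

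On eligibility, inclusion criterion 5 (Protocol 5.1) requires "No evidence of a lymphoproliferative malignancy or other autoimmune-related underlying conditions", and Protocol 5 adds that "Deviations from eligibility criteria are not allowed". SAP sections 1 and 3 describe the population in the same way. Inclusion criterion 2 defines the AIHA types by DAT and cold agglutinin findings; for CAD it reads "Cold (CAD): DAT positive for C3d only, with cold agglutinins of I specificity".

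**The concern.** There are two problems in the same short section. One named subgroup contradicts the eligibility criteria. The baseline variable that decides whether a participant can show a change in DAT for IgG is left out.

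The second matters more. CAD participants are IgG-negative at entry, and the two cohorts are meant to enrol different proportions of them. If DAT for IgG is shown only overall and by initial dose, a difference between the 1 mg and 2.5 mg cohorts could come from who was enrolled and not from the drug. Type is also central to the sponsor's purpose. Cohort 2 was composed to evaluate CAD better (Protocol 2.6 and 4.1), and SAP 10.1 says the interim analysis was added partly with a possible Phase 3 plan for CAD in view.

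**Working it through.** **The plan's own figures.** The documents give no number for the PD analysis. The only design probabilities are for seeing at least one adverse event of interest at a 20% rate. They reproduce (1 − 0.8^10 = 0.893; 1 − 0.8^15 = 0.965), but nothing here depends on them.

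**Step 1: size of the named subgroup.** Criterion 5 excludes other autoimmune disease and eligibility deviations are ruled out, so the planned size is 0. The only route in is a participant found ineligible after enrolment, which Protocol 7.1.1 handles case by case.

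**Step 2: which types carry each marker at entry (inclusion criterion 2).**

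| Type | DAT for IgG | Cold agglutinins |
|---|---|---|
| Warm (2a) | positive | not stated |
| CAD (2b) | negative | present |
| Mixed (2c) | positive | present, high titer |

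**Step 3: planned mix (Protocol 4.1, SAP 3).** Cohort 1 has 10 participants, at most 3 of them CAD or mixed, so 7 to 10 are warm. Cohort 2 is taken as 15 participants: 5 CAD, 8 warm and 2 of any type. Counting over every mix that fits:

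| | Cohort 1 | Cohort 2 | Overall |
|---|---|---|---|
| DAT-IgG positive at entry (warm + mixed) | 7-10 of 10 | 8-10 of 15 | 15-20 of 25 |
| Type requires cold agglutinins (CAD + mixed) | 0-3 of 10 | 5-7 of 15 | 5-10 of 25 |

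**Step 4: effect on a pooled summary.** Let *s* be the share carrying the marker at entry and *r* the change among carriers, with no change in the rest. The pooled change is *s* × *r*. Suppose *r* is the same in both cohorts, so that dose has no effect.

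- DAT for IgG: 0.70*r* to 1.00*r* in Cohort 1, 0.53*r* to 0.67*r* in Cohort 2, and 0.60*r* to 0.80*r* overall. The gap in favour of Cohort 1 runs from 0.70 − 0.67 = 0.03*r* to 1.00 − 0.53 = 0.47*r*.
- Cold agglutinins, **assuming** warm participants have none: 0 to 0.30*r* in Cohort 1, 0.33*r* to 0.47*r* in Cohort 2, and 0.20*r* to 0.40*r* overall. The gap now favours Cohort 2.

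Case mix alone can therefore push the two markers in opposite directions.

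**Step 5: sensitivity to the mix.** The Cohort 2 numbers are approximate. With 4 CAD participants instead of 5, carriers of DAT-IgG could be 11 of 15 (73%), which exceeds the Cohort 1 minimum of 70%, so the direction of the gap is likely but not guaranteed. With fewer than 8 warm participants, the CAD share could be higher than shown.

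**Step 6: is type handled elsewhere?** Appendix A of the SAP lists no table or listing by AIHA type, and none titled for DAT, cold agglutinins or complement. Section 7.7 is the only analysis text for these three.

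**The case against.** The case for leaving the section alone has several parts.

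- The subgroup list opens with the word including, and AIHA type is a defined baseline characteristic. A reader might infer that a split by type is ruled out. It is only unspecified. That stands, but an unnamed split is also not a planned one.
- A reader might infer that cold agglutinins cannot change in warm AIHA by definition. The documents do not support this: criterion 2a defines warm disease by DAT alone and does not require cold agglutinins to be absent. Only DAT for IgG in CAD is settled by definition.
- A reader might infer that the PD endpoint as a whole is diluted. The type definitions do not show this for reticulocytes, DAT for complement, haptoglobin, bilirubin, LDH, CH50, C3 or C4. At most two markers are affected.
- If DAT is reported as positive or negative, SAP 5.1 gives counts and percentages, so the baseline negatives would be visible. This is partly right. Counts by visit do show how many were negative at the start, but pooled rows do not show how many of the initial positives converted.
- All analyses are exploratory (SAP 3.2). The cohorts are sequential and not randomized, and Cohort 1 participants may escalate to the Cohort 2 dose after Week 6. Splitting by type would not make the dose contrast clean. That stands. It would remove one known and avoidable source of difference.
- An empty subgroup biases nothing. Also true; this half of the point is a contradiction to correct.

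**Conclusion.** The point holds in a limited form. The subgroup by coexisting autoimmune disease is empty by design and contradicts the eligibility criteria. Omitting AIHA type makes a pooled DAT-IgG summary depend on case mix: under the planned mix it shows 70-100% of the carriers' change in Cohort 1 and 53-67% in Cohort 2. For cold agglutinins the corresponding figures, 0-30% and 33-47%, hold only if warm participants have none.

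These ranges assume that the planned enrolment is met and that non-carriers do not change. The consequence is for reading descriptive summaries of secondary markers. No primary endpoint, hypothesis test, stopping rule or sample size is affected.

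**What to change.** In SAP 7.7:

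- Replace concomitant autoimmune disease with AIHA type (warm, CAD, mixed).
- Summarize change in DAT for IgG, and change in cold agglutinins, among participants positive for that marker at baseline. State what counts as positive, and give n by cohort and type.

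Restricting to baseline positives also settles the open question about cold agglutinins in warm disease without any assumption. Protocol Table 1 schedules both tests for all participants at screening and Week 12, and type is already collected, so no new data are needed.

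The cost is small denominators, above all for cold agglutinins in Cohort 1, where only 0 to 3 CAD or mixed participants are planned; individual values may be the more useful display there. A log scale for titers and a split of complement by type are optional preferences and are not needed to resolve this point.

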8. SAFETY AND TOLERABILITY

Sample data displays are provided in [Appendix A](#).

8.1. General Considerations

The analyses in this section will be provided for the FAS in the treatment period and TE evaluable population in the extension period. Safety tables will be summarized for the treatment period and extension period separately.

Summary tables may be replaced with listings when appropriate. For instance, an AE frequency table may be replaced with a listing if it only contains a few unique PTs reported on relatively few participants.

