4. STUDY DESIGN

4.1. Overall Design

This is a multicenter, open-label study designed to evaluate the safety and efficacy of INCB050465 administered orally to participants with AIHA who have decreased hemoglobin and evidence of ongoing hemolysis that requires treatment intervention. Participants with primary warm, cold (CAD), and mixed-type AIHA without an underlying lymphoproliferative malignancy or autoimmune related hemolytic anemia and have failed at least 1 prior treatment for AIHA will be eligible for enrollment. Participants will be treated for 12 weeks. There are 2 cohorts in this study: Cohort 1, with up to 10 participants, with no more than 3 cold (CAD)/mixed-type AIHA participants to appropriately reflect response in the overall population, which is predominantly warm AIHA; and Cohort 2, with approximately 15 participants, with approximately 5 CAD AIHA, up to 8 warm AIHA, and the remainder from any of the 3 AIHA types. Cohort 2 distribution and increased number of participants are intended to better evaluate CAD AIHA patients and possible signal observed in Cohort 1, as well as account for higher baseline variability seen in the wAIHA subpopulation. The first cohort (Cohort 1, n = 10participants) enrolled will initially receive INCB050465 1 mg QD. At Week 6, participants who continue to require transfusions or do not attain a meaningful clinical response (at least a stabilization ≥ 2 g/dL increase in hemoglobin from baseline to Week 6) may have their dose increased, with sponsor preapproval, to 2.5 mg QD of INCB050465 until Week 12 (see Section 6.6). If there are any tolerability issues in individual participants who received 2.5 mg, the dose may be decreased to 1 mg. Following enrollment of a minimum of 6 warm AIHA participants in the first cohort and review of safety and efficacy through Week 6, Cohort 2 may begin enrollment. Participants in Cohort 2 (n \approx 15) will receive INCB050465 2.5 mg QD for 12 weeks. If there are any tolerability issues, the dose may be decreased to 1 mg. The investigator and sponsor should review and agree any dose increases or decreases. Following the last dose of INCB050465, participants will be eligible for a 12-week (3 months) follow-up for evaluation of the safety and durability of response.

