An internal Safety Review Committee (see Section 9.6) will review clinical response and AE data. If there is no clinical response (CR or PR) by Week 12 in the first cohort of 10 participants, including those who receive dose escalation to 2.5 mg, the study will be stopped for futility. If there is a clear emerging signal from either Cohort 1 or Cohort 2, the committee may make recommendations as to the expanded study of either cohort to obtain additional safety and efficacy data at either dose level.

Participants who complete the 12-week treatment period and demonstrate clinical benefit from study drug may enter into an extension period with sponsor approval to continue receiving INCB050465 until the drug is available through another clinical study, or is commercially available, or the sponsor stops the study or the study drug development. Visits during the extension period will be conducted every 8 to 12 weeks to continue to monitor the effectiveness of the clinical response, as well as clinical safety laboratory assessments and adverse events.

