5.3.2. Treatment Extension Evaluable Population

Participants who apply at least 1 dose of INCB050465 in the extension period will constitute the TE evaluable population.

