8.2.2. Adverse Events of Special Interest

Adverse events of special interest will be summarized in the following categories by treatment and extension periods separately:

- Colitis
- CMV infection
- Diarrhea
- Exfoliative dermatitis
- Febrile neutropenia
- Herpes simplex
- Intestinal perforation
- PJP
- Pneumonia
- Pneumonitis
- Rash
- Varicella zoster virus infection

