8.2.3. Adverse Event Summaries

An overall summary of AEs will include:

- Number (%) of participants reporting any TEAEs.
- Number (%) of participants reporting any SAEs.
- Number (%) of participants reporting any Grade 3 or 4 TEAEs.
- Number (%) of participants who had a TEAE leading to death.
- Number (%) of participants reporting any treatment-related TEAEs.
- Number (%) of participants who temporarily interrupted study treatment because of TEAEs.
- Number (%) of participants who permanently discontinued study treatment because of TEAEs.

The following summaries will be produced by MedDRA term (if 2 or fewer participants appear in a table, a listing may be appropriate):

- Summary of TEAEs by SOC and PT.
- Summary of TEAEs by PT in decreasing order of frequency.
- Summary of TEAEs by SOC, PT, and maximum severity.
- Summary of treatment-related AEs by SOC and PT.

- Summary of treatment-related AEs by PT in decreasing order of frequency.
- Summary of treatment-related AEs by SOC, PT, and maximum severity.
- Summary of Grade 3 or 4 TEAEs by SOC and PT.
- Summary of Grade 3 or 4 treatment-related TEAEs by SOC and PT.
- Summary of TEAEs leading to death by SOC and PT.
- Summary of treatment-emergent SAEs by SOC and PT.
- Summary of treatment-emergent SAEs by PT in descending order of frequency.
- Summary of treatment-related SAEs by SOC and PT.
- Summary of TEAEs leading to dose interruption by SOC and PT.
- Summary of TEAEs leading to discontinuation of treatment by SOC and PT.
- Summary of nonserious TEAEs by SOC and PT.
- Summary of AESI by SOC and PT.

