3.5 ECG		
3.5.1.X	Summary of 12-Lead ECG: PR Interval Values	FAS
3.5.2.X	Summary of 12-Lead ECG: QRS Interval Values	FAS
3.5.3.X	Summary of 12-Lead ECG: QT Interval Values	FAS
3.5.4.X	Summary of 12-Lead ECG: QTcB Interval Values	FAS
3.5.5.X	Summary of 12-Lead ECG: QTcF Interval Values	FAS
3.5.6.X	Summary of 12-Lead ECG: RR Interval Values	FAS

Note: For tables ending with "X," separate tables will be provided for the treatment period (FAS) and extension period (TE).

Listings

Listing No.	Title
Demographic and Baseline Characteristics	
1.1.1	Participant Enrollment and Disposition Status
1.1.2	Participant Inclusion and Exclusion Criteria Violations
1.1.3	Protocol Deviations
1.2.1	Demographic

Listing No.	Title
1.2.2	Baseline Disease Characteristics
1.3	General Medical History
1.4.1	Prior and Concomitant Medications
1.4.2	Prior Medications for AIHA
1.5	Study Drug Compliance
Efficacy	
2.1	Hemoglobin
2.2	Transfusion
2.3	Daily Usage of Prednisone
2.4	FACIT-F Subscale
Adverse Events and Exposure	
3.2.1	Adverse Events
3.2.2	Serious Adverse Events
3.2.3	Grade 3 or 4 Adverse Events
3.2.4	Adverse Events Leading to Death
3.2.5	Treatment-Related Adverse Events
3.2.6	Adverse Events Leading to Interruption of Study Drug
3.2.7	Adverse Events Leading to Discontinuation of Study Drug
Laboratory Data	
3.3.1	Clinical Laboratory Values – Hematology
3.3.2	Clinical Laboratory Values – Serum Chemistry
3.3.3	Abnormal Clinical Laboratory Values – Hematology
3.3.4	Abnormal Clinical Laboratory Values – Serum Chemistry
Vital Signs	
3.4.1	Vital Signs
3.4.2	Abnormal Vital Sign Values
3.4.3	Alert Vital Sign Values
ECG	
3.5.1	12-Lead ECG Values
3.5.2	Abnormal 12-Lead ECG Values
3.5.3	Alert 12-Lead ECG Values

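### Extension-period AE and AESI tables give crude percentages over open-ended, probably unequal follow-up, and no planned table counts each participant once over the whole time on drug

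*SAP*

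**What the plan says.** SAP 8.1 fixes the layout: "Safety tables will be summarized for the treatment period and extension period separately". SAP 8.2.2 repeats it for the events of special interest: "Adverse events of special interest will be summarized in the following categories by treatment and extension periods separately". The closing note to the tables in SAP Appendix A gives each safety table exactly these two versions and no pooled one.

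The measure is a proportion of participants, for example "Number (%) of participants reporting any TEAEs" (SAP 8.2.3). The grouping is in SAP 5.2: "Participants will be summarized overall and based on the dose regimen initially assigned in the study". The extension denominator is a head count: "Participants who apply at least 1 dose of INCB050465 in the extension period will constitute the TE evaluable population" (SAP 5.3.2).

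Extension dosing continues "until the drug is available through another clinical study, or is commercially available, or the sponsor stops the study or the study drug development" (Protocol 4.1). Cohort 2 may open only "Following enrollment of a minimum of 6 warm AIHA participants in the first cohort and review of safety and efficacy through Week 6" (Protocol 4.1). SAP 9 places an interim analysis at the point when everyone has completed Week 12. SAP 8.2.1 counts an event as treatment-emergent up to 30 days after the last dose, so the window grows with time on drug.

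SAP 6.4 does plan an exposure summary (duration, average daily dose, total dose) for both populations. It measures duration from Day 1, and no event table uses it as a denominator.

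**The concern.** A crude percentage answers a clear question only when everyone is watched for about the same time. In the extension, follow-up depends on entry date, on when a participant stops, and on the data cut. At the interim cut the last entrant has little or no extension time, while earlier entrants may have much more. Two cohorts with the same underlying event rate can then show different percentages, and neither can be set beside the 12-week figure.

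The second gap does not depend on which cohort was followed longer. A participant with the same type of event in both periods appears in both tables, and the tables have different denominators. The number of participants who ever had the event on drug is not shown.

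Safety is a primary objective. SAP 10.1 says that the interim analysis is meant to support publications and a possible Phase 3 plan, so the tables are likely to be quoted.

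**Working it through.** **The plan's own safety figure.** SAP 3.3 gives the chance of seeing at least one event at a 20% underlying rate. 1 − 0.8^10 = 0.8926, which is above 89%; 1 − 0.8^15 = 0.9648, which is above 96%. Both reproduce. The 20% has no time unit, so it does not describe incidence over an open-ended period.

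**Inputs for the illustration.** The documents give no extension exposure by cohort and no event rate per unit time. Both are assumed here. The true rate λ is constant and the same in both cohorts; t is mean extension exposure, treated as common within a cohort.

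**Formulas.** Crude incidence = 1 − exp(−λt). Expected time at risk to first event = (1 − exp(−λt))/λ. The person-time rate is the first divided by the second, which equals λ whatever t is.

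**Results with t = 2 years (Cohort 1) and 0.75 years (Cohort 2):**

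| λ per participant-year | Cohort 1 | Cohort 2 | Crude difference | Rate in both |
|---|---|---|---|---|
| 0.1 | 1 − exp(−0.2) = 18.1% | 1 − exp(−0.075) = 7.2% | 10.9 points | 0.1 |
| 0.2 | 1 − exp(−0.4) = 33.0% | 1 − exp(−0.15) = 13.9% | 19.0 points | 0.2 |
| 0.4 | 1 − exp(−0.8) = 55.1% | 1 − exp(−0.3) = 25.9% | 29.2 points | 0.4 |

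**Varying the exposure gap.** At a hazard of 20% per 52 weeks (λ = −ln 0.8 = 0.223 per year):
- 104 versus 26 weeks gives 36.0% versus 10.6%, a gap of 25.4 points.
- 52 versus 26 weeks gives 20.0% versus 10.6%, a gap of 9.4 points.
- 26 versus 12 weeks gives 10.6% versus 5.0%, a gap of about 5.5 points.

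Equal exposure gives no difference. Swapping the exposures reverses the sign.

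**Against the 12-week period.** At λ = 0.2, 12 weeks gives 1 − exp(−0.2 × 12/52) = 4.5%, ignoring the 30-day tail. The same rate would thus show as 4.5% in the treatment table and 13.9% or 33.0% in the extension table.

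**Whole-exposure count.** Let a participants have the event in the treatment period, b in the extension and c in both. Total incidence on drug is (a + b − c)/N, where N is the full analysis set. The planned tables give a, b and N but not c, so the total cannot be recovered from them.

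**The case against.** The case against is substantial, and much of it stands.

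- **Separate periods are partly a safeguard.** They keep open-ended time out of the 12-week tables, where both cohorts have the same planned duration. This stands: the comparability problem is confined to the extension tables.
- **Exposure is reported and events are listed.** Under SAP 6.4 a reader would see unequal durations. But duration from Day 1 is not extension time at risk, and no rate follows from the planned tables.
- **Longer follow-up of Cohort 1 is inferred.** The extension was added only at Protocol Amendment 3, and early stopping could shrink or reverse the gap. Protocol 4.2 expected all accrual within 12 to 18 months, so the assumed 15-month gap (2 − 0.75 = 1.25 years) is large against that plan. Amendment 5 cites pandemic effects on enrollment, so a long gap is possible, but it is not documented.
- **No cohort comparison is planned.** Analyses are exploratory and unrandomised. The planned mix of AIHA types differs between cohorts, Cohort 1 participants raised to 2.5 mg stay under their initial regimen, and extension participants are selected for benefit. Person-time rates remove none of this.
- **Precision will be poor.** As an assumed example, 1 event in 10 participant-years is 0.10 per year, with an exact 95% interval of about 0.003 to 0.56. That is a reason to show the interval; a bare percentage hides the same imprecision.
- **Ascertainment differs.** Extension visits are every 8 to 12 weeks, against every 1 to 2 weeks on treatment, and Protocol 8.3 words AE recording differently for the extension. A pooled rate for any TEAE would mix the two, so the additions should centre on SAEs, Grade 3-4 TEAEs and AESIs.

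**Conclusion.** The point holds for the extension tables and for the missing whole-exposure count. Extension percentages by initial cohort are not comparable with each other or with the 12-week period, and total on-drug incidence cannot be read from the plan's outputs. The effect is on interpretation; no hypothesis is tested, so no error rate is involved.

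The 11 to 29 points rest entirely on the assumed exposures and rates, equal true hazards and a constant rate. They show what unequal follow-up alone can produce; they do not estimate what happened in this trial.

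A reader might infer more in three ways that the documents do not support:
- That the tables will make the 1 mg cohort look less safe. No follow-up by cohort is given, so even the direction is unknown.
- That the 12-week tables share the problem. Their planned duration is common to both cohorts.
- That person-time rates would recover a dose relation. Dose increase, AIHA type and selection into the extension would still confound it.

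This is a low-cost improvement to safety reporting. It does not show that the planned safety analysis is invalid.

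**What to change.** In SAP 8.2.2, 8.2.3 and Appendix A:

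1. For the extension, show participant-years at risk and first-event rates per participant-year with exact Poisson 95% intervals for SAEs, Grade 3-4 TEAEs and each AESI category, overall and by initial cohort. Count time at risk from the first extension dose to the first event in the extension, or otherwise to the end of the treatment-emergent window or the data cut.
2. Add one table for each of these categories covering first dose to last dose + 30 days, counting each participant once.
3. Keep the separate period tables.
4. Add a footnote that the cohort rates are not a dose comparison and that event ascertainment differs between the periods.

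The cost is SAP wording and a few tables, since event start dates and dosing dates are already collected. The downsides are wide intervals at this sample size, a constant-rate assumption that may not fit participants who have already completed 12 weeks on drug, and mixed ascertainment in the whole-exposure tables.
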